APPENDIX

1. Amendments to the Protocol	12
2. Amendments to the Statistical Analysis Plan	13

PROTOCOL Version 1.3 (See Table of Amendments)

Multi-Center Randomized Controlled Trial of Refeeding in Anorexia Nervosa

1. Introduction

Current recommendations to guide the clinical care of AN patients hospitalized with medical instability due to malnutrition are based solely on retrospective or observational studies and/or clinical experience. No studies to date have prospectively tested high calorie refeeding (HCR) and the long-term impact on recovery is unknown. Consensus has developed over recent decades that patient safety can only be guaranteed using low calorie refeeding (LCR). The entrenchment of clinical practice without supporting evidence is a widely recognized dilemma in healthcare. While RCTs are considered the “gold standard” to establish evidence-based medicine, until recently there was insufficient data to propose such a study of refeeding in AN. We now have preliminary findings to indicate that LCR might be too cautious and that HCR appears feasible and may improve long-term recovery. Thus, we are poised to compare these two treatments in a parallel, randomized fashion.

2. Study Design

The purpose of this multi-center randomized controlled trial is to compare LCR vs. HCR refeeding strategies for hospitalized adolescents with AN. Participants will be recruited upon hospital admission at two centers (UCSF and Stanford) to maximize sample size, and randomly assigned 1:1 within site to one of the two strategies. A total of 120 participants age 12-24 yrs who meet DSM-5 diagnostic criteria for AN and atypical AN and present as medically unstable due to malnutrition will be enrolled. Treatments will not be blinded, since both the patients and clinicians who work with this population are highly skilled at estimating kcal and would be able to determine their group assignment by simply viewing the meal trays. In addition, target kcal will be reached faster in HCR and this would be apparent on physician orders. The proposed study is powered to detect a meaningful difference in clinical remission (Aim 1A).

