AIM 2: Safety of LCR vs. HCR during initial hospitalization. We hypothesize that LCR and HCR will *not* differ by *incidence of* 2A) hypophosphatemia (<3 mg/dL), 2B) hypomagnesaemia (≤ 1.7 mg/dL), and 2C) hypokalemia (<3.5 mEq/L).

AIM 3: Cost-effectiveness (CE) of LCR vs. HCR. We hypothesize that HCR will be more cost-effective than LCR, as determined by cost (including costs of initial and re-hospitalizations, 12 mo follow-up, other care, and safety/adverse events (AEs) and effectiveness per adolescent recovered (defined in AIM 1A and B).

2. Statistical Methods

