2.2. Outcomes

The primary analysis of the study adopts a modified intent-to-treat (mITT) approach to compare outcomes between randomized HCR and LCR participants who received treatment for at least one day. Patients who are ineligible post randomization, provide no assent after parent's consent, or withdraw before receiving any treatment, will not be included in the mITT analysis for reasons of data unavailability, ethics and clinical relevance. Sensitivity analyses will be conducted to check that 1) withdrawal patients are not different from patients in both groups included in mITT in baseline covariates; and 2) including withdrawal patients in the analyses will not change results and conclusion of mITT analyses. The sensitivity analyses will provide us

reassurance of mITT results.

Aim 1A: Primary (long-term) efficacy outcome. A (generalized) linear mixed-effects regression model (GLMM) will compare study arms with respect to achievement and maintenance of clinical remission. Clinical remission is defined as the combination of mBMI and EDE-Q score at mo 1,3,6,12 (separate analyses below) and measured at 1, 3, 6, and 12 months as 1) clinically remitted (yes or no) and 2) weight recovered (percent of mBMI). The models will include time, treatment group, time*treatment group interaction, and unbalanced baseline covariates if any as fixed effects, while sites and patients will be included as random effects to account for the correlation due to clustering. The time*treatment group interaction provides mITT effect of HCR compared to LCR on clinical remission over time. The average remission rates and scores and their 95% confidence intervals (CIs) will be estimated from the model. GLMM accounts for the fluctuating nature of mBMI and EDE-Q in AN and uses all available data with missing at random assumption, instead of a stronger assumption of missing completely at random required in other models. Aim 1 models will be supplemented with secondary analyses: (i) potential moderators at baseline (included in regression models as main effects and interactions with period and time), may include DSM-5 criteria and EDE-Q thresholds of risk and (ii) potential mediators at follow-up (included as time-dependent covariates), may include food recall (DDS and DVS), healthcare utilization, or incidence of AEs. In addition, separate mixed-effects models will analyze continuous versions of mBMI and EDE-Q to describe longitudinal trajectories.

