Aim 1B: Secondary (short-term) efficacy outcome: Time to restore and maintain medical stability in hospital is defined as days to reverse the medical instability indicators for hospitalization in adolescents with eating disorders. A six-point index will adjudicate daily medical stability: 1.) 24-hour heart rate (HR) ≥ 45 bpm, 2.) systolic blood pressure (SBP) ≥ 90 mmHg, 3.) temperature $\geq 35.6^\circ$ C, 4.) orthostatic increase in HR ≤ 35 bpm, 5.) orthostatic decrease in systolic BP ≤ 20 mmHg, and 6.) $\geq 75\%$ of mBMI. Each of the six criteria were scored as "1" if met, "0" if unmet and missing (not scored) if not measured. Medical stability was considered restored when all criteria were stable for 24 hours, allowing a maximum of two missing values (i.e. participants were considered stable if meeting 4 of 4, 5 of 5 or 6 of 6 measured criteria). All randomized participants who receive at least one day of treatment, including those who withdraw at any time during the refeeding intervention, will be included in the mITT analysis. Specifically, survival analysis with log rank test will compare time to achieve medical stability by arm while accounting for the correlation within sites; participants who do not meet stability criteria by hospital discharge will be right-censored. In case of any important unbalanced covariate at baseline, Cox proportional hazard ratio model will be used to control for the potential bias due to the confounder. Additionally efficacy outcomes will include the proportion achieving medical stability in each arm, change in %mBMI as compared to baseline, and time to restore HR.

Aim 2. Safety: Primary indicator of safety will be incidence of the following electrolyte abnormalities during hospitalization: 2A) hypophosphatemia (<3 mg/dL), 2B) hypomagnesaemia (≤ 1.7 mg/dL), 2C) hypokalemia (< 3.5 mEq/L). These AEs will be tracked, recorded, reported to the DSMB for monitoring, and to the IRB and NIH as needed, according to the attached DSMP. Incidence of the electrolyte abnormalities and proportion receiving supplementation to correct electrolyte abnormalities will be compared by arm during hospitalization using Fisher's exact test. Additional safety outcomes: the proportion receiving electrolyte supplementation during the hospitalization between groups will be compared with Fisher's exact test; time to electrolyte nadir will be compared with Wilcoxon rank sum test.

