2.3. Power and Sample-size Considerations

Aim 1. Based on studies of AN remission, **Table 2.A** shows that with $N=60$ per arm we have 80% power on 2-sided 0.05-level test to detect a 20% difference (8% vs. 28%) if data were cross-sectional ($\rho=1$). Our longitudinal data will allow detection of smaller effects, especially if the correlation among outcomes is low ($\rho < 0.8$). We anticipate 85% retention and non-differential dropout by arm. Since **time to medical stability** is also expected to differ by at least 12% (**Table 2.B.**), we will be adequately powered for Aim 1B.

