2.2 Outcomes	
Amendment 1: End-point for AIM 1B shortened to in hospital treatment period
 
Rationale: To match the timeframe for the safety outcome and to better capture the efficacy of this relatively short intervention (less than 2 weeks in hospital) within a long, open follow-up trial. Further, to allow timely dissemination of findings. [Citation: IOM guideline, Sharing Clinical Trial Data: Maximizing Benefits, Minimizing Risk, pg 118: Investigators “may publish the primary trial endpoints despite ongoing longer-term participant follow-up; in this case, the last participant’s last visit may not occur for some time, and hence the full analyzable data set may not be complete at the time of the original publication.”]
 
Timeframe for AIM 1B specified as 2 weeks and posted on clinicaltrials.gov
 
Project officer, [name] approved analysis of short-term (in-hospital) outcomes by arm (DSMB notified 7/03/19, randomization code was broken)
 
Short-term database locked
	06/30/2015 05/26/2019 07/31/2019
2.2 Outcomes	
Amendment 2: Analytic approach for AIM 1B changed from mixed effects regression modeling to survival analysis
 
Rationale: survival analysis chosen to examine time to restore medical stability in hospital (amended AIM 1B), rather than mixed effects regression modeling to examine medical stability over 12-month follow-up. This is a more appropriate approach to assess “time to” outcome, which accounts for the variable lengths of hospital stay and allows participants who were discharged before medical stability was restored to be right-censored.
 
Change in “time to” analysis documented in NIH Progress Report
 
Data Coordination Center documented decision to use survival analyses for AIM 1B
	05/05/2017 10/17/2017
2.2 Outcomes	
Amendment 3: Analytic approach for AIM 2 (safety) changed from Cox regression modeling to basic non-parametric testing
 
Rationale: Originally planned approach (Cox regression models) assumed high incidence electrolyte abnormalities based on prior studies reporting rates up to 48%. However, ongoing AE monitoring during the trial revealed very low incidence and therefore basic parametric methods were chosen to allow clinical interpretation of the results.
 
DSMB reports since 2017 (signed by DSMB members and sent to POs, [name] and [name])
	02/17/2017 02/20/2018 02/15/2019

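### Aim 2 predicts no difference in electrolyte abnormalities, but incidence is compared only by Fisher's exact test, with no interval, margin or power, so a non-significant result cannot support the prediction

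*Combined protocol and SAP*

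**What the plan says.** SAP section 1 states the safety hypothesis as an absence of difference: "We hypothesize that LCR and HCR will *not* differ by *incidence of* 2A) hypophosphatemia", and likewise for hypomagnesaemia and hypokalemia. SAP 2.2 (Aim 2) makes in-hospital incidence of these abnormalities the primary indicator of safety. It names one between-arm analysis for incidence: "Incidence of the electrolyte abnormalities and proportion receiving supplementation to correct electrolyte abnormalities will be compared by arm during hospitalization using" Fisher's exact test. The other Aim 2 comparisons are also tests of difference: Fisher's test for the proportion supplemented and a Wilcoxon rank sum test for time to nadir.

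Intervals are planned elsewhere. For Aim 1A, SAP 2.2 says "The average remission rates and scores and their 95% confidence intervals (CIs) will be estimated from the model".

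Power is discussed for Aim 1 only. Protocol section 2 says "The proposed study is powered to detect a meaningful difference in clinical remission (Aim 1A", and SAP 2.3 ends with the statement that "we will be adequately powered for Aim 1B".

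Appendix Table 2, Amendment 3, explains why Cox regression was dropped for Aim 2. The earlier approach "assumed high incidence electrolyte abnormalities based on prior studies reporting rates up to 48" percent, but "ongoing AE monitoring during the trial revealed very low incidence and therefore basic parametric methods were chosen". The amendment adds no effect measure, interval, margin or power.

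**The concern.** A test of difference can contradict a hypothesis of no difference, but it cannot support it. A p-value above 0.05 may mean that the arms are close, or that the trial was too small to see a gap. Nothing else planned for incidence separates these two readings.

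This matters because electrolyte safety is the counterweight to any benefit of higher-calorie refeeding. If the Aim 2 result is summarised as no significant difference, readers will tend to take it as equal safety whether or not the data justify that.

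The low incidence noted in Amendment 3 cuts both ways. For a fixed ratio of risks it weakens the test. For an absolute risk difference it narrows the interval, so an interval could give real reassurance. That interval is not planned.

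**Working it through.** **Inputs from the documents.** 60 per arm and a two-sided 0.05 level (SAP 2.3); 1:1 allocation, N = 120 (protocol section 2). Aim 2 is an in-hospital endpoint, so 60 per arm is used as the best case.

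**Inputs assumed.** Appendix Table 2 gives only prior rates of up to 48% and an unquantified very low incidence during the trial. Control rates from 1% to 48% are therefore assumptions, as are the 10- and 15-point yardsticks.

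**The plan's own power figure.** None exists for Aim 2. The nearest is 80% for 8% vs 28% in SAP 2.3. With the pooled-variance formula:

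- mean rate = (0.08 + 0.28)/2 = 0.18
- SE under the null = √(2 × 0.18 × 0.82/60) = 0.0701
- SE under the alternative = √((0.08 × 0.92 + 0.28 × 0.72)/60) = 0.0677
- z = (0.20 − 1.96 × 0.0701)/0.0677 = 0.92, so power is 82%

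This agrees with a claim of at least 80%. Exact Fisher power for the same rates is 77%.

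**Fisher's test for Aim 2.** Power is the sum, over all 61 × 61 pairs of counts (a, b), of Bin(a; 60, p_LCR) × Bin(b; 60, p_HCR) wherever the two-sided Fisher p is at most 0.05. The last column is the chance that the upper 95% Newcombe limit for HCR minus LCR lies below 10 points, which would be a wrong exclusion here.

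| True rates, LCR vs HCR | Fisher power | P(p > 0.05) | P(upper limit < 10 points) |
|---|---|---|---|
| 2% vs 12% | 43% | 57% | 2% |
| 5% vs 15% | 33% | 67% | 2% |
| 10% vs 20% | 25% | 75% | 2% |
| 48% vs 58% | 16% | 84% | 3% |

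For a doubling of risk, power is 1% (2 vs 4%) and 9% (5 vs 10%). For a 20-point excess at low rates it is 93% (2 vs 22%) and 85% (5 vs 25%).

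**What the interval gives when true rates are equal.**

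| Common true rate | P(upper limit < 10 points) | P(upper limit < 15 points) |
|---|---|---|
| 1% | 92% | >99% |
| 2% | 83% | 99% |
| 3% | 73% | 96% |
| 5% | 58% | 89% |
| 10% | 40% | 75% |
| 48% | 21% | 39% |

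**Two non-significant results that mean different things.** The Newcombe limits combine the Wilson limits (l, u) of each arm: lower = d − √((p_H − l_H)² + (u_L − p_L)²), upper = d + √((u_H − p_H)² + (p_L − l_L)²).

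- LCR 3/60, HCR 9/60: the Wilson limits are 0.017 to 0.137 and 0.081 to 0.261, and d = 0.10. Lower = 0.10 − √(0.069² + 0.087²) = −0.011. Upper = 0.10 + √(0.111² + 0.033²) = 0.216. Fisher p = 0.13, and the interval is −1.1 to +21.6 points.
- 1/60 in each arm: Fisher p = 1.0, and the interval is −7.3 to +7.3 points.

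The test labels both results non-significant. Only the second limits the possible excess to less than 10 points.

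**The case against.** The plan does not claim equivalence or non-inferiority, and it nowhere says that p > 0.05 will be read as equal safety. Fisher's test is a sound choice for sparse counts, and a reader could compute an interval from the reported counts. The 10-point yardstick is not in the documents. The design differences they do state run from 12 to 20 points, for other endpoints, and at low incidence Fisher's test would detect a 20-point excess in 85% to 93% of trials. The 48% rows rest on a planning rate that Amendment 3 says was not borne out, and 10% is hard to call very low. The data safety monitoring plan mentioned in SAP 2.2 is not in the supplied text, so any thresholds in it could not be checked.

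Most of this is fair as far as it goes. The test is not wrong, and a gross excess would probably be seen. The low-rate rows deserve the most weight, and there p > 0.05 still occurs in 57% to 67% of trials with a true 10-point excess. No document treats 20 points as an acceptable electrolyte excess either. What does not stand is the suggestion that the gap is harmless. A stated hypothesis needs an analysis that can support it, and leaving readers to derive the interval leaves the p-value to frame the primary safety conclusion.

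**Conclusion.** The concern holds. For incidence, the primary safety indicator, the plan offers a p-value as the only between-arm evidence on a hypothesis of no difference. Under the low rates that best fit Amendment 3 (2% to 5% in the control arm), a real 10-point excess would go undeclared in about six to seven trials in ten. At equal true rates of 1% to 5%, an interval would exclude that excess in 58% to 92% of trials. These sizes rest on assumed rates, 60 evaluable patients per arm and a 10-point yardstick chosen for illustration. The logical point needs none of those assumptions. This should be changed, but it does not invalidate the planned test.

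**What to change.** In SAP 2.2, Aim 2, add for each of the three electrolytes the HCR minus LCR risk difference with a Newcombe 95% interval (or one named exact method), beside the planned Fisher p-value. State that p > 0.05 will not be interpreted as equal safety, and that the Aim 2 result will be described by the excess that the upper limit excludes.

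Date the addition. Appendix Table 2, Amendment 1, records "DSMB notified 7/03/19, randomization code was broken" and a later lock of the short-term database, so any margin introduced since then must be labelled post hoc. The interval itself needs no margin.

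The cost is a few sentences in the SAP and one extra line per electrolyte, from counts that Fisher's test already requires. The downside is that the safety conclusion may have to be stated as inconclusive.

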A high energy liquid supplement ("formula") providing 1.5 kcal per mL (360 kcal per 240 mL can) will be used orally as needed to replace kcal refused in meals or snacks per a standard calorie replacement protocol. We previously reported a greater than 98% concordance between kcal prescribed and actual kcal ingested using this method, as well as an equal proportion of kcal intake from formula in LCR and HCR groups. This finding supports our clinical observation that HCR meals can be completed without additional reliance on drinking formula. However, most AN patients do experience discomfort during refeeding and therefore all participants will receive SOC meal support including emotional support and techniques such as distraction. All beverages will be weighed and measured before placement on the tray, with a 1.5 L per day free water restriction. Room sitters will observe intake of all meals/snacks and remain in the room for 45 min afterwards.

c. Monitoring of electrolytes: Blood for electrolytes will be obtained between 5 and 7 am every 24hr for the first 7 days and more frequently if needed. Since the risk of refeeding decreases after the first week, electrolytes will be monitored every other day starting on day 8 unless there is continued evidence of abnormalities.

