e. Study time points: Participants will be followed prospectively in hospital with daily measures of calorie and supplement intake and weight from admission through discharge. Patients will be discharged when medically stable, with the primary criterion of heart rate ≥ 45 bpm for least 24 hr. Full medical stability defined as HR ≥ 45 bpm for 24 hrs, temperature ≥ 35.6°C for 24 hrs, ≥ 75% of mBMI, BP ≥ 90/45 mmHg for 24 hrs or if systolic BP < 90 then asymptomatic and all else stable, orthostatic change in HR ≤ 35 bpm or if > 35 then asymptomatic and all else stable; and orthostatic change in SBP ≤ 20 mmHg or if > 20 then asymptomatic and all else stable.

Timing of Procedures: Table 1

	INPATIENT			OUTPATIENT FOLLOW---UP				
	Admit	Daily	DC*	10 dy	1 Mo	3 Mo	6 Mo	12 Mo
MEDICINE/NURSING PROCEDURES								
Weight	SOC	SOC	SOC	X	X	X	X	X
Height	SOC			X	X	X	X	X
Vital Signs	SOC	SOC	SOC	X	X	X	X	X
Electrolyte monitoring ¥	SOC	X	SOC					
NUTRITION PROCEDURES								
24---hr food recall	X			X	X	X	X	X
QUESTIONNAIRE ADMINISTRATION								
EDE-Q	X		X		X	X	X	X
HCUMS survey				X	X	X	X	X
Demogr & Eating Disorder	X							

Follow-up form				X	X	X	X	X
----------------	--	--	--	---	---	---	---	---

* DC = discharge; SOC = Standard Of Care; Rnd = Randomization; ¥ SOC is every other day; we will monitor daily as part of Aim 2.

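### Aim 2 compares electrolyte abnormalities over each patient's own stay; if stays differ by arm, the shorter-stay arm is observed for less time, and a common day-7 comparison should be added

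*Combined protocol and SAP*

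**What the plan says.** SAP section 2.2, Aim 2, defines the outcome over the stay: "Primary indicator of safety will be incidence of the following electrolyte abnormalities during hospitalization". The three abnormalities are low phosphorus, low magnesium and low potassium. On the method it says "Incidence of the electrolyte abnormalities and proportion receiving supplementation to correct electrolyte abnormalities will be compared by arm during hospitalization", with Fisher's exact test. No fixed window, person-time or censoring rule is given. SAP section 1 hypothesises that the arms do not differ on these outcomes and states no margin.

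Several other places determine how long a patient is observed:

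- **Draws in hospital.** Protocol section 3.1.c: "Blood for electrolytes will be obtained between 5 and 7 am every 24hr for the first 7 days and more frequently if needed". It continues: "Since the risk of refeeding decreases after the first week, electrolytes will be monitored every other day starting on day 8", unless abnormalities persist. The footnote to Table 1 says monitoring is daily for Aim 2 and mentions no change at day 8.
- **Draws after discharge.** None. The electrolyte row of Table 1 is marked only at admission, daily in hospital and at discharge.
- **Discharge.** Protocol section 3.1.e: "Patients will be discharged when medically stable, with the primary criterion of heart rate" at or above a threshold for 24 hours.
- **Expected arm difference.** Aim 1 hypothesises that medical stability differs by arm. Table 2.B shows the HCR figure above the LCR figure in every row.

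In SAP Appendix Table 2, Amendment 2 adopts survival analysis for Aim 1B because it "accounts for the variable lengths of hospital stay". Amendment 3 replaces Cox regression for Aim 2 with simple tests because few abnormalities were being seen.

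**The concern.** An ever/never proportion compares risk cleanly only when both arms are observed for the same time. Here observation ends at an event that the trial expects treatment to affect. A patient who leaves early without an abnormality counts the same as one followed twice as long. The mITT set includes anyone treated for at least one day, so early withdrawals count this way too.

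The direction matters. If HCR stays are shorter, its incidence is lowered by shorter observation, and a higher daily risk could appear as similar incidence. With no margin, a non-significant Fisher test is likely to be read as support for equal safety.

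The plan recognises variable stays for Aim 1B but makes no allowance for them in Aim 2. Low incidence is a reason not to fit a Cox model. It is not a reason to leave the observation windows unaligned.

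**Working it through.** The plan gives no power, margin or expected incidence by arm for Aim 2, so there is no figure of its own to reproduce.

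**Inputs from the documents.** Draws are daily on days 1 to 7 and every other day from day 8 (section 3.1.c), or daily throughout (Table 1 footnote). Risk is said to fall after week 1 (section 3.1.c). Stays are under two weeks (Amendment 1).

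**Assumptions.** Stays of 12 days (LCR) and 9 days (HCR), and the incidence levels and shapes of daily risk below.

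**Step 1: draws per patient.** Under section 3.1.c, 12 days gives 7 draws plus days 8, 10 and 12, so 10 draws. Nine days gives 7 plus day 8, so 8 draws. Under the Table 1 footnote the counts are 12 and 9.

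**Step 2: equal risk per draw.** Incidence = 1 − (1 − h)^draws, with h = 2% in both arms.

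- Section 3.1.c: 1 − 0.98^10 = 18.3% and 1 − 0.98^8 = 14.9%, a gap of 3.4 points with no true difference.
- Table 1 footnote: 1 − 0.98^12 = 21.5% and 1 − 0.98^9 = 16.6%, a gap of 4.9 points.

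An excess in HCR risk per draw of about 10/8 − 1 = 25% (first schedule) or 12/9 − 1 = 33% (second) would be fully hidden.

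**Step 3: let risk fall after week 1.** Let r be the daily risk after day 7 relative to week 1. Exposure to day d (d ≥ 7) is E(d) = 7 + r(d − 7). If LCR incidence is p, HCR incidence with equal true risk is 1 − (1 − p)^(E(9)/E(12)).

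| Risk after day 7 | E(9)/E(12) | HCR when LCR is 20% | False gap at LCR 20% | At LCR 10% | At LCR 48% | Hidden hazard ratio |
|---|---|---|---|---|---|---|
| Same (r = 1) | 9/12 | 15.4% | 4.6 points | 2.4 | 9.2 | 1.33 |
| One quarter (r = 0.25) | 7.5/8.25 | 18.4% | 1.6 points | 0.9 | 3.2 | 1.10 |
| None (r = 0) | 7/7 | 20.0% | 0 | 0 | 0 | 1.00 |

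The 48% column uses the highest prior rate quoted in Amendment 3.

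The zero row needs every stay to reach day 7. With stays of 10 and 5 days and no risk after day 7, HCR would show 1 − 0.8^(5/7) = 14.7% against 20%, a false gap of 5.3 points.

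**Step 4: what a common window recovers.** Suppose the true HCR hazard ratio is 1.5, risk is constant, and LCR is 20% over 12 days.

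- Whole stay: HCR = 1 − 0.8^(1.5 × 9/12) = 22.2% against 20.0%, a gap of 2.2 points.
- By day 7: HCR = 1 − 0.8^(1.5 × 7/12) = 17.7% against LCR = 1 − 0.8^(7/12) = 12.2%, a gap of 5.5 points.

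**Step 5: is a patient-day rate better?** Take equal risk, all in week 1, 20% in each arm. Daily hazard is −ln(0.8)/7 = 0.0319. Event-free days per patient to day 7 are 0.2/0.0319, about 6.27. The 80% still event-free then add 0.8 × 5 = 4.0 days in LCR and 0.8 × 2 = 1.6 days in HCR. Rates are 0.2/10.27 and 0.2/7.87 per day, an HCR/LCR ratio of 1.30 with no true difference. With r = 0.25 the ratio is about 1.20. Under front-loaded risk the rate is therefore biased against HCR.

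**The case against.** The strongest reply is that incidence during hospitalization is a legitimate outcome. Treatment is limited to the hospital stay (protocol section 3.3), and a shorter course is part of the strategy being tested. That stands. The whole-stay proportion answers a sensible question and should be kept. But it mixes risk per day with time observed, and it cannot alone support a claim that refeeding faster carries no more risk per day.

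A second reply is that the protocol states that risk falls after week 1 and samples most densely then. This also stands, and it removes much of the effect when stays exceed seven days. It does not remove it when stays end sooner or when late risk remains. On the section 3.1.a schedule (1400 kcal plus 200 kcal every other day), LCR reaches HCR's starting level of 2000 kcal only on day 7, so later LCR risk cannot be assumed absent.

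Third, Amendment 3 reports very low incidence. The absolute gap is then small: at 5% in LCR, constant risk gives 5.0% against 3.8%, about 1.2 points, or less than one patient in 60. The relative distortion is much the same.

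Fourth, the SAP also compares time to electrolyte nadir and summarises length of stay. These help a reader judge the problem but do not correct the incidence comparison.

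A reader might infer that the plan is known to flatter HCR, or that a hazard excess of one third would be hidden. The documents support neither. They give no stay by arm, the direction is inferred from Table 2.B and the discharge rule, and one third requires constant risk with daily sampling or continuous detection throughout.

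**Conclusion.** The concern holds as a conditional one. Aim 2's main comparison has an observation window that treatment may change, and the plan makes no allowance for it. For assumed stays of 12 and 9 days with equal true risk, the false gap at 20% LCR incidence runs from 0 to 4.6 points, and is about 1.6 points if late risk is a quarter of week-1 risk. It is larger if stays in one arm end within week 1 and smaller at lower incidence. Whichever arm stays less time looks safer; that this is HCR is an inference.

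A reader might conclude that a rate per patient-day should replace the Fisher test. That does not follow. With risk concentrated in week 1, as the protocol describes, the rate gives a spurious HCR/LCR ratio of about 1.2 to 1.3. A common early window is the sounder addition.

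**What to change.** For each of 2A to 2C:

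- Add a comparison of the proportion with a first abnormality by day 7 from the start of study refeeding, reported as a risk difference with a 95% CI. Treat patients discharged or withdrawn before day 7 as censored, and give their number by arm, because discharge on stability may be informative. An exact interval applies directly if everyone is observed to day 7. If some are censored, take the day-7 estimates and their interval from a Kaplan-Meier analysis.
- Show cumulative incidence by day over the whole stay.
- Report the number of electrolyte draws and the length of stay by arm.
- Keep the whole-stay Fisher comparison and interpret it beside these results.
- Do not make a rate per patient-day the main analysis.

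Reconcile protocol section 3.1.c (every other day from day 8) with the Table 1 footnote (daily), since the two give different draw counts.

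The cost is SAP wording and one extra analysis of dated results already collected. Appendix Table 2 records that the randomization code has been broken and the short-term database locked, so the addition should be labelled as supplementary. Its limitation is that a day-7 window misses later abnormalities; the cumulative incidence curve is there to show them.
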